#### **F. Assessment of response:**

In this study, the combination of tenofovir and emtricitabine and tenofovir monotherapy will be evaluated for long-term effects on chronic hepatitis B in both HBeAg-positive and -negative cohorts and in treatment naïve and those with resistance to lamivudine, adefovir, entecavir or all agents.

Definitions:

- a) **Full virological response:** absence of detectable HBV DNA by PCR ( $<10^2$  IU/ml)
- b) **Partial virological response:** suppression of HBV DNA to  $<10^4$  IU/ml but  $>10^2$  IU/ml
- c) **Serological response (HBeAg-positive patients only):** loss of detectable HBeAg.
- d) **Full biochemical response:** fall of serum ALT into the normal range ( $<41$  IU/L)
- e) **Partial histological response:** improvement in liver histology as defined by a decrease in the inflammatory component of the histological activity index (HAI) score by 3 points or more and no worsening of the Ishak fibrosis score. Histological responses will be assessed after 48 and 192 weeks of therapy.
- f) **Complete histological response:** improvement in liver histology as defined by a decrease in the inflammatory component of the histological activity index (HAI) score by 3 points or more and no worsening of the Ishak fibrosis score and a decrease of the HAI score to 3 or less. Histological responses will be assessed after 48 and 192 weeks of therapy.
- g) **Combined response:** the combination of a virological, serological, biochemical and histological response.
- h) **Complete Response:** Loss of HBsAg. A complete response is the major focus and most hoped for outcome of long-term antiviral treatment of hepatitis B. A complete response is reason for stopping all antiviral treatment.

Beneficial responses are also characterized as initial, maintained or sustained:

- a) **Initial response:** full virological or biochemical response occurring within the first 24 weeks of therapy.

- b) **Maintained response:** virological, serological, biochemical, histological, or combined response present at the time of last observation in a patient still receiving therapy.
- c) **Sustained response:** virological, serological, biochemical, histological or combined response present at the time of last observation and at least six months after stopping therapy.

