The primary study endpoints will be a maintained full virological response after 48 weeks and 192 weeks of therapy (the two points of formal statistical analysis). The major secondary endpoint will be absence of a failure of therapy and absence of resistance mutations. Other endpoints to therapy will be loss of HBeAg, loss of HBsAg, normalization of serum ALT, improvements in histology activity index, improvements in hepatic fibrosis, improvement in Fibroscan scores and decrease in HVPg. Other endpoints will be improvement in symptom scores at 48 and 192 weeks.

Failure of therapy may be due to primary non-response, lack of virological response, breakthrough, or relapse, as defined below.

A **primary non-response** is defined as lack of decrease in HBV DNA levels by at least 1  $\log_{10}$  after at least 24 weeks of therapy in the absence of non-compliance.

A **failure in virological response** is defined as failure to suppress HBV DNA below  $10^4$  IU/ml after 48 weeks of therapy in the absence of non-compliance.

A **breakthrough** is defined as a  $\geq 1 \log_{10}$  IU/L increase in HBV DNA level from nadir in two consecutive samples at least one month apart in a patient with an initial full virological response in the absence of non-compliance.

A **relapse** is defined as a rise in HBV DNA levels to above  $10^4$  IU/ml or of ALT to above the normal range after therapy is stopped in a patient who previously had a maintained full virological response.

These definitions are all interlocking but help to define response and non-response rates and whether therapy has a sustained effect.

**Stopping therapy:** Therapy will be continued indefinitely or until one of the following endpoints are reached:

1. **Failure of therapy:** If HBV DNA levels remain consistently  $>10^4$  IU/ml after one year of continuous therapy, patients will be offered alternative therapy or the option to stop therapy. Alternative therapies may include switching to combination therapy if they were receiving monotherapy or switching to entecavir if receiving combination therapy. Patients who fail to respond may also elect to receive a course of peginterferon. These options are available at the NIH Clinical Center on an open-label basis.

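### Two failure definitions in the major secondary endpoint need rewording: a suppressed patient can count as a primary non-responder, and breakthrough may miss rebounds after late suppression

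*Combined protocol and SAP*

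**What the plan says.** All definitions are in Section F (Assessment of response) of the combined protocol and SAP unless stated.

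- **Endpoint.** "The major secondary endpoint will be absence of a failure of therapy and absence of resistance mutations".
- **Routes to failure.** "Failure of therapy may be due to primary non-response, lack of virological response, breakthrough, or relapse, as defined below".
- **Primary non-response.** HBV DNA has not fallen by at least 1 log10 "after at least 24 weeks of therapy in the absence of non-compliance".
- **Failure in virological response.** HBV DNA not brought below 10^4 IU/ml after 48 weeks.
- **Breakthrough.** A confirmed rise of at least 1 log10 from nadir "in a patient with an initial full virological response in the absence of non-compliance".
- **Relapse.** A rise "after therapy is stopped in a patient who previously had a maintained full virological response".
- **Response terms.** Full virological response is undetectable HBV DNA, given as below 10^2 IU/ml. "Partial virological response" covers values between 10^2 and 10^4. An initial response is a "full virological or biochemical response occurring within the first 24 weeks of therapy".
- **Entry levels.** Section A2 admits nucleoside-experienced patients above 10^2 IU/ml. Section A.3 admits relapsers above 10^3. Section A1 requires above 10^4 for naïve patients, or above 10^3 with cirrhosis.
- **Detection limit.** Section C (Initial evaluation) gives 20 IU/ml; the Précis gives 10^2 IU/ml.

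**The concern.** The four definitions decide who counts as a failure in an endpoint the protocol calls major.

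(a) Full response is an absolute level and primary non-response is a relative fall. When the entry value is low, both can be true of the same patient. Low entry values are plausible in Groups C and D: the Background describes incomplete suppression on previous nucleoside therapy, and Section D keeps resistant patients on their pre-study drugs until randomization.

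(b) The word *initial* in the breakthrough definition is also a defined term with a 24-week limit. Read that way, two patients with the same on-drug rebound are classed differently only because one was first suppressed sooner, and the earlier suppressor gets the worse class.

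At stake is a failure count that contradicts the response count for some patients, and that leaves classification choices open until the data are in hand.

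**Working it through.** **The plan's own figure.** Section I states 86% power for Fisher's exact test with 94% against 70%, 50 per arm, two-sided 0.05. Exact enumeration over both binomial distributions gives 0.857, so the figure reproduces. It concerns the primary endpoint and plays no part below.

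**(a) Primary non-response against full response**

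Let B be the entry value and V the on-treatment value, in IU/ml. A full response needs V < 100. Primary non-response needs log10(B/V) < 1, that is V > B/10. Both hold when B/10 < V < 100, which is possible only if B < 1,000.

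Examples:
- 500 to 80: log10(500/80) = 0.80
- 300 to 50: log10(300/50) = 0.78
- 150 to 20: log10(150/20) = 0.88

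Whole-number values, from the 20 IU/ml limit up, that are both a full response and a primary non-response:

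| Entry B | On-treatment V |
|---|---|
| 101–199 | 20–99 (all) |
| 300 | 31–99 |
| 500 | 51–99 |
| 800 | 81–99 |
| 990 or more | none |

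For entry below 200, even a fall to 20 IU/ml is under 1 log10: log10(199/20) = 0.998.

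For entry above 10^3 there is no overlap: log10(1001/99) = 1.005. That clears Groups A, B and E.

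The table assumes that below 10^2 is what defines full response. Two other readings make the conflict depend on how an undetectable result is scored. If it is scored at s, it cannot show a 1 log10 fall when B < 10s. The scores below are assumptions, since the documents state none.

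- *Detectable* means the 20 IU/ml limit, so values of 20–99 are not full responses. With s = 10, the condition is B < 100, and no eligible patient is exposed. With s = 20, entries of 101–199 are exposed.
- 10^2 is the detection limit, so values below it are not separately seen. With s = 50, entries of 101–499 are exposed. With s = 100, entries of 101–999 are exposed.

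Exposure ceiling: Groups C and D are capped at 20 each, so 20 + 20 = 40. Section D also gives the entry levels for Groups C and D as above 10^2 and 10^3 respectively. Read literally, that leaves only Group C, up to 20, although Section D's own Group D entry and Section A2 both say 10^2.

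**(b) The same rebound, two classes**

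Both illustrative patients enter at 50,000 IU/ml and remain on drug.

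| Week | Late suppressor | Early suppressor |
|---|---|---|
| 24 | 5,000 | 80 |
| 36 | 80 | 900 |
| 48 | 900 | 2,000 |
| 60 | 2,000 | – |

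Rises from nadir: log10(900/80) = 1.05 and log10(2000/80) = 1.40, in two consecutive samples.

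Late suppressor, rule by rule:
- Primary non-response: no. log10(50000/5000) = 1.00 at week 24, and log10(50000/2000) = 1.40 at week 60.
- Failure in virological response: no. HBV DNA is below 10^4.
- Relapse: no. Therapy has not stopped.
- Breakthrough: no, if *initial* means within 24 weeks.

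The early suppressor is a breakthrough. Nothing nearby closes the gap. The stopping rule headed failure of therapy applies "If HBV DNA levels remain consistently" above 10^4 IU/ml, phenotypic resistance in Section H also needs a rise above 10^4, and the endpoint's resistance component counts mutations only. Both patients are partial virological responders by level, and both already count as non-responders on the primary endpoint at week 48.

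**Weight of one patient.** One reclassification moves an arm's rate by 100/50 = 2 points at 50 per arm, or 100/20 = 5 points if Groups C and D (20 per arm) are reported alone.

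**The case against.** The strongest reply is to (b). *Initial* may simply mean that suppression came before the rebound, and on that reading the gap disappears. This stands as a limit on confidence. Against it, Section F defines initial, maintained and sustained together, and the relapse definition uses *maintained*, so taking *initial* as the defined term is the natural reading.

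On (a), primary non-response is judged after at least 24 weeks, not only at week 24. A patient at 80 from an entry of 500 who later falls to 50 or below has the 1 log10 decrease, so the conflict may be temporary. That is fair, though the text does not say whether a later fall cancels the earlier class. The unresolved detection limit also stands: the overlap at 20–99 IU/ml belongs to one reading only. That reading has some support, because partial response starts above 10^2, so otherwise values of 20–99 would be neither full nor partial.

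Section F says the definitions interlock and that failure *may* have these causes. Acknowledged overlap among failure types does not make a full responder a failure by design, nor does it tell an analyst how to class the late rebound.

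A reader might go further and treat the compliance clauses as a defect, since a viremic non-compliant patient in follow-up escapes three of the four definitions while a dropout is a failure under Section I. The documents do not support calling that an error. It may be a deliberate measure of drug failure, and Section H has a similar clause.

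**Conclusion.** The point holds and is minor. Confidence is high for (a) and moderate for (b), which rests on *initial* carrying its Section F meaning.

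For (a), at most 40 patients are exposed, or 20 on the literal Section D reading. How many actually enter below 10^3 IU/ml is not given and could be very few. For (b), no count can be derived.

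A reader might infer that the trial's main result is compromised. It is not: the primary endpoint uses the full-response level alone, and its 86% power and the resistance-mutation component do not depend on these rules.

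A reader might also infer a bias towards one arm. The documents show no direction. Entry values precede randomization, so exposure to (a) is balanced in expectation, and the protocol's first hypothesis expects similar HBV DNA declines in both arms.

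Nor does it follow from the 24-week limit that many rebounds go uncounted. In the protocol's own experience with seven patients on tenofovir, all were below 10^2 within 24 weeks. The series is small, but it suggests that late first suppression may be uncommon.

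**What to change.** For endpoint classification only:

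1. Add to primary non-response: *and HBV DNA still at or above 10^2 IU/ml*. State how an undetectable result is scored, and which detection limit (20 or 10^2 IU/ml) applies.
2. Define breakthrough after any full virological response on therapy, by deleting *initial*.

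**Cost.** No new measurements are needed, because Section E already has HBV DNA taken at every visit. Primary non-responses may fall slightly and breakthroughs may rise slightly. Section O sends samples for susceptibility testing once virologic breakthrough is identified, so a wider definition could mean somewhat more shipments.

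**Timing.** Make the change before any comparison by arm. The Protocol section describes the trial as unblinded (Section D says double-blind), so a later change would be open to the charge of being post hoc.

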## **G. Assessment of Toxicity and modification of dose of tenofovir and emtricitabine**

### **The risks and hazards of tenofovir therapy**

There is limited experience with the use of tenofovir in patients with chronic hepatitis B. More than 12,000 HIV positive patients have been treated with tenofovir alone or in combination with other antiretroviral drugs for periods of 28 days to 215 weeks in Phase I-III clinical trials and expanded access studies. A total of 1,544 patients have received tenofovir 300 mg once daily in Phase I-III clinical trials; over 11,000 patients have received tenofovir in expanded access programs. In study 903, a double-blind, active controlled multicenter study comparing tenofovir 300 mg daily administered in combination with lamivudine and efavirenz versus stavudine (d4T), lamivudine and efavirenz in 600 antiretroviral naïve patients, the most common adverse reactions seen were mild to moderate gastrointestinal events and dizziness. Mild adverse events (Grade 1) were common with a similar incidence in both arms and included dizziness, diarrhea and nausea. Selected treatment emergent moderate to severe adverse events (Grades 2-4) reported in  $\geq 5\%$  of the tenofovir versus non-tenofovir arms respectively, included headache 14% vs. 17%, pain 13% vs. 12%, fever 8% vs. 7%, abdominal pain 7% vs. 12%, back pain 9% vs. 8%, asthenia 6% vs. 7%, diarrhea 11% vs. 13%, nausea 8% vs. 9%, dyspepsia 4% vs. 5%, vomiting 5% vs. 9%, lipodystrophy 1% vs. 8%, arthralgias 5% vs. 7%, myalgias 3% vs. 5%, depression 11% vs. 10%, insomnia 5% vs. 8%, dizziness 3% vs. 6%, peripheral neuropathy 1% vs. 5%, anxiety 6% vs. 6%, pneumonia 5% vs. 5%, rash 18% vs. 12%. With the exception of fasting cholesterol and fasting triglyceride elevations that were more common in the stavudine group (40% and 9%) compared with tenofovir (19% and 1%) respectively, laboratory abnormalities observed in study 903 occurred with similar frequency in the tenofovir and non-tenofovir treatment arms. Grade 3/4 laboratory abnormalities reported in  $\geq 1\%$  of treated patients include creatinine kinase 12% vs. 12%, serum amylase 9% vs. 8%, serum AST 5% vs. 7%, serum ALT 4% vs. 5%, hematuria ( $>100$  RBC's/HPF) 7% vs. 7% and neutropenia ( $<750/\text{mm}^3$ ) 3% vs. 1%. In

study 934, 511 antiretroviral naïve patients received either tenofovir and emtricitabine administered in combination with efavirenz or zidovudine/lamivudine administered in combination with efavirenz. Adverse events and laboratory abnormalities observed in this study were generally consistent with those seen in previous studies in treatment-experienced or treatment naïve patients. In addition to adverse events reported from clinical trials, the following events have been identified during post-approval use of tenofovir. Because they are reported from a population of unknown size, estimates of frequency cannot be made. These events include allergic reactions, hypophosphatemia, lactic acidosis, dyspnoea, abdominal pain, increased amylase, pancreatitis, increased liver enzymes, hepatitis, renal insufficiency, renal failure, acute renal failure, Fanconi syndrome, proximal tubulopathy, proteinuria, increased creatinine, acute tubular necrosis, nephrogenic diabetes insipidus, polyuria and nephritis.

Tenofovir has a black box warning indicating that lactic acidosis and severe hepatomegaly with steatosis including death have been reported with the use of nucleoside analogues alone or in combination with other antiretrovirals. Additionally severe acute exacerbations of hepatitis B have been reported in patients who are coinfecting with HBV and HIV and have discontinued tenofovir. Tenofovir is principally eliminated by the kidney. The dosing interval needs to be adjusted in all patients with creatinine clearance <50 ml/min.

The majority of safety data on tenofovir has come from HIV populations on multidrug regimens. The few series of patients with chronic hepatitis B treated with tenofovir have not reported any serious side effects. The major safety concern with tenofovir is renal impairment. Cases of acute renal failure and Fanconi syndrome (renal tubular injury with severe hypophosphatemia) have been reported in association with the use of tenofovir. The majority of these cases occurred in patients with underlying systemic or renal disease, or in patients taking nephrotoxic agents, however, some cases occurred in patients without identified risk factors.

One other potential problem identified with the use of tenofovir in the HIV population is a decline in bone mineral density. In a 144-week study of HIV positive treatment naïve patients, decreases in bone mineral density (BMD) were seen at the lumbar spine and hip in both arms of the study (study 903 see above). At Week 144, there was a significantly greater mean percentage decrease from baseline in BMD at the lumbar spine in patients receiving tenofovir plus lamivudine plus efavirenz compared with patients receiving stavudine plus lamivudine plus efavirenz. Changes in BMD at the hip were similar between the two treatment groups. In both groups, the majority of the reduction in BMD occurred in the first 24–48 weeks of the study and this reduction was sustained through 144 weeks. Twenty-eight percent of tenofovir-treated patients vs. 21% of the comparator patients lost at least 5% of BMD at the spine or 7% of BMD at the hip. Clinically relevant fractures (excluding fingers and toes) were reported in 4 patients in the tenofovir group and 6 patients in the comparator group. Tenofovir disoproxil fumarate was associated with significant increases in biochemical markers of bone metabolism (serum bone-specific alkaline phosphatase, serum osteocalcin, serum C-telopeptide, and urinary N-telopeptide), suggesting increased bone turnover. Serum parathyroid hormone levels

and 1,25 Vitamin D levels were also higher in patients receiving tenofovir. The effects of tenofovir-associated changes in BMD and biochemical markers on long-term bone health and future fracture risk are unknown.

The risk of carcinogenesis, mutagenesis and impairment in fertility has been studied. Long-term oral carcinogenicity studies of tenofovir in mice and rats were carried out at exposures up to approximately 16 times (mice) and 5 times (rats) those observed in humans at the therapeutic dose for HIV infection. At the high dose in female mice, liver adenomas were increased at exposures 16 times that in humans. In rats, the study was negative for carcinogenic findings at exposures up to 5 times that observed in humans at the therapeutic dose.

Tenofovir was mutagenic in the in vitro mouse lymphoma assay and negative in an in vitro bacterial mutagenicity test (Ames test). In an in vivo mouse micronucleus assay tenofovir was negative when administered to male mice.

There were no effects on fertility, mating performance or early embryogenic development when tenofovir was administered to male rats at a dose equivalent to 10 times the human dose based on body surface area comparisons for 28 days prior to mating and to female rats for 15 days prior to mating through day seven of gestation. There was however an alteration of the estrous cycle in female rats.

Reproduction studies have been performed in rats and rabbits at doses up to 14 and 19 times the human dose based on the body surface area comparisons and revealed no evidence of impaired fertility or harm to the fetus due to tenofovir. There are however, no adequate and well-controlled studies in pregnant women.

Women of child bearing potential will have a pregnancy test at each study visit. They will be counseled to use at least two forms of adequate birth control while receiving study medications. Any female patient found to be pregnant will stop antiviral therapy and be followed in the Liver Diseases Clinic.

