### Protocol

Up to 100 patients with chronic hepatitis B will be enrolled including at least 40 patients who have not been previously treated (naïve patients: primary study) and up to 40 patients who have received or are receiving nucleoside analogue therapy and up to 20 patients who have relapsed following withdrawal of therapy (experienced patients: salvage study). After medical evaluation and liver biopsy, patients will be randomized and receive either monotherapy with tenofovir (300 mg) daily or combination therapy with tenofovir (300 mg) and emtricitabine (FTC: 200 mg) daily. Gilead Sciences will provide the combination of tenofovir and emtricitabine as a single tablet and tenofovir 300 mg as a single tablet. Neither the investigators nor the patients will be blinded to the investigational agents. Patients will be followed carefully on therapy at 2 to 12 week intervals and undergo repeat medical evaluation and liver biopsy at 48 and 192 weeks. Therapy will be continued indefinitely, although the randomized phase of this trial will last for 192 weeks only. The definition of a successful endpoint of therapy will be the maintained suppression of HBV DNA below  $10^2$  IU/ml by current PCR-based assays, Roche Amplicor assay). Secondary endpoints will be (2) normalization of ALT levels and (3) histological improvements which are expected to occur in all patients with full suppression of HBV DNA and in a proportion of those with partial suppression. Other endpoints will be (3) loss of HBeAg and (4) loss of HBsAg. Patients who have lost HBsAg will undergo a monitored withdrawal of therapy with reinstatement of treatment if relapse occurs.

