### B. Exclusion criteria

- 1) Previous or current treatment with tenofovir or emtricitabine.
- 2) Co-infection with HDV as defined by the presence of anti-HDV in serum and/or HDV antigen in the liver.
- 3) Co-infection with HCV as defined by the presence of HCV RNA in serum.
- 4) Co-infection with HIV as defined by the presence of anti-HIV in serum.
- 5) Decompensated liver disease as defined by serum bilirubin >2.5 mg/dL (with direct bilirubin > 0.5 mg/dL), prothrombin time of greater than 2 seconds prolonged, a serum albumin of less than 3 g/dL, or a history of ascites, variceal bleeding or hepatic encephalopathy.
- 6) Presence of other causes of liver disease, (i.e. hemochromatosis, Wilson disease, alcoholic liver disease, nonalcoholic steatohepatitis, alpha-1-anti-trypsin deficiency).
- 7) A history of organ transplantation or in the absence of organ transplantation, any immunosuppressive therapy requiring the use of more than 5 mg of prednisone (or its equivalent) daily.
- 8) Significant systemic illness other than liver diseases including congestive heart failure, renal failure, chronic pancreatitis, diabetes mellitus with poor control that in the opinion of the investigator may interfere with therapy.
- 9) Pregnancy or inability to practice contraception in patients capable of bearing or fathering children and lactating women.
- 10) Hepatocellular carcinoma (HCC), or the presence of a mass on imaging studies of the liver that is suggest of HCC, or an alpha-fetoprotein level of greater than 500 ng/mL.
- 11) History of clinically apparent pancreatitis or evidence of subclinical pancreatitis as shown by serum amylase values twice the upper limits of the normal range and abnormalities of the pancreas on CT or other imaging studies of the abdomen.
- 12) Sensory or motor neuropathy apparent from medical history and physical examination.
- 13) Creatinine clearance < 50 ml/min, serum creatinine > 1.3 mg/dl or urine protein >1 gram/24-hours; creatinine clearance will be determined on the average of two 24 hour urine specimens. Accuracy of collection will be ensured by documenting

- appropriate total creatinine excretion in the 24-hour urine specimen (15 mg/kg) and correcting for the patient's age, gender and body surface area.

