### **E. Monitoring**

Patients will be seen, interviewed, and have blood and urine tests taken at regular intervals according to the following schedule (Appendix A): on at least two occasions during the six months before treatment (Screen 1 and 2) including at the time of liver biopsy and initial evaluation, on day 0 (before first administration of drug) and at weeks 2, 4, 8, 12, 24, 36, and 48 after starting therapy. Thereafter, the patients will be seen every 12 weeks while on therapy. At each visit, the patients will be asked about symptoms and possible side effects and fill out a symptom and side effect questionnaire. Blood samples will be drawn for CBC and biochemical tests including chemistry-20 panel (ALT, AST, alkaline phosphatase, creatine kinase, lactic dehydrogenase, direct and total bilirubin, sodium, potassium, chloride, bicarbonate, glucose, BUN, creatinine, albumin, total protein, calcium, and phosphate), and 10 ml of research blood. HBV DNA will be measured at every clinical visit during therapy and more often if needed, such as to investigate viral breakthrough. In addition, HBsAg, HBeAg and anti-HBe will be tested every 12 weeks during therapy and anti-HBs if appropriate. An additional sample will be collected for routine storage to allow for repeat testing. Urine will be collected for urinalysis and random total protein/creatinine ratio at every visit. Twenty-four hour urine for creatinine clearance and total protein will be done at 48 weeks and 192 weeks. Women of child bearing potential will have a pregnancy test at each study visit. Women with a positive pregnancy test will be immediately withdrawn from study drug/s. Patients may be offered alternative approved therapy if clinically indicated. Immunological testing for CD4+ and CD8+ T cell responses to HBV antigens will be done before treatment for all previously untreated patients and repeated at 2, 4, 8, 12, 36 and 48 weeks for HLA-A2 positive patients. Alpha-fetoprotein levels will be measured every 24 weeks. Ultrasound or computerized tomography of the liver will be done every 24 weeks months in patients with advanced fibrosis or cirrhosis; in other patients these tests will be done at the time of 48 and 192 week liver biopsies. Fibroscan of the liver will be performed yearly. Bone mineral density will be re-assessed at 48 and 192 weeks.

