A major safety concern with tenofovir is renal impairment. Cases of acute renal failure and Fanconi syndrome (renal tubular injury with severe hypophosphatemia) have been reported in association with the use of tenofovir. The majority of these cases occurred in patients with underlying systemic or renal disease, or in patients taking nephrotoxic agents, however, some cases occurred in patients without identified risk factors. Patients will be monitored by a series of tests for renal toxicity including calculated GFR using the Modification of Diet in Renal Disease (MDRD) formula, urine analysis and serum phosphate. Dose adjustments or cessation will be based upon any of the following criteria:

1) Absolute decline in GFR by 25 mls/min/1.73 m^2 confirmed on two occasions 2 weeks apart. GFR will be calculated using the Modification of Diet in Renal Disease (MDRD)

formula: (MDRD GFR (ml/min/1.73m^2=170 x[PCr]-0.999 X [Age]-0.176 X [.0762 if patient is female] X [1.180 if patient is black] X [SUN]-0.170 X[Alb]+0.318 where PCr=serum creatinine concentration (mg/dl) (alkaline picrate method); SUN=serum urea nitrogen concentration (mg/dl) (urease method); Alb=serum albumin concentration (g/dl) (bromocresol green method)).

2) Abnormality in any one of the following 4 parameters calculated GFR, urine glucose, serum phosphate and a routine urine analysis will trigger a formal renal evaluation. This will include including assessment of GFR by 24 urine hour creatinine clearance, urine glucose, fractional excretion of phosphate, 24 hour urine for amino acids and serum uric acid, If the evaluation is consistent with Fanconi's syndrome, patients will be discontinued from therapy indefinitely.

3) For Grade 1 toxicity serum creatinine  $\geq .5$  above baseline, the patient will be monitored weekly until the creatinine returns to baseline or  $\leq 0.3$  mg/dL of the baseline value. For confirmed Grade 2 and  $\geq 0.5$  increases from baseline, therapy will be permanently discontinued.

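### Section G says tenofovir's dosing interval must change below a creatinine clearance of 50 ml/min, but its renal dose-adjustment criteria do not use that level and no adjusted interval is given

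*Combined protocol and SAP*

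**What the plan says.** Section G covers toxicity and dose modification. Its text on the risks of tenofovir states, for every patient: "The dosing interval needs to be adjusted in all patients with creatinine clearance <50 ml/min". Its text on the risks of combination therapy then introduces a list: "Dose adjustments or cessation will be based upon any of the following criteria". The list has three items:

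1. "Absolute decline in GFR by 25 mls/min/1.73" m², calculated by the MDRD formula and confirmed on two occasions two weeks apart.
2. An abnormality in any one of "calculated GFR, urine glucose, serum phosphate and a routine urine analysis will trigger a formal renal evaluation". That evaluation includes a 24-hour creatinine clearance. Therapy ends if the findings fit Fanconi's syndrome; no other result has a stated consequence.
3. A creatinine rise of at least 0.5 mg/dl above baseline. At Grade 1 this means weekly monitoring; at confirmed Grade 2 with such a rise, permanent discontinuation.

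Four other places bear on the point:

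- The Protocol section gives fixed daily dosing: "monotherapy with tenofovir (300 mg) daily or combination therapy with tenofovir (300 mg) and emtricitabine (FTC: 200 mg) daily".
- Section B, item 13, excludes patients with "Creatinine clearance < 50 ml/min, serum creatinine > 1.3 mg/dl or urine protein >1 gram/24-hours".
- Section E schedules the measured clearance: "Twenty-four hour urine for creatinine clearance and total protein will be done at 48 weeks and 192 weeks".
- Section F, under stopping for toxicity, makes a decline in kidney function a ground for stopping. It sets no threshold and sends the reader to the combination-therapy text for management.

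**The concern.** One part of Section G names a renal level at which dosing must change. The part that is meant to drive dose changes does not use that level. Neither part says what the changed interval would be. The exclusion criterion applies the 50 ml/min level at entry only, so it does not settle what happens when a patient crosses it on treatment.

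The protocol calls renal impairment the major safety concern with tenofovir, and tenofovir is given in both arms for 192 weeks or longer. Two investigators could manage the same patient differently, each with support in the text. Section F counts a stop for toxicity as failure of therapy, and absence of failure is the major secondary endpoint. Inconsistent handling could therefore also change how a patient's outcome is classified.

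**Working it through.** The plan gives no figure to reproduce. The check is whether an eligible patient can pass below 50 without meeting criterion 1 or criterion 3.

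**Inputs from the protocol.** Entry needs a clearance of at least 50 ml/min and creatinine of at most 1.3 mg/dl (Section B, item 13). Criterion 1 is a fall of 25 units. Criterion 3 begins at a rise of 0.5 mg/dl. The GFR formula is printed in Section G.

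**Assumptions.** Non-black man, so no sex or race multiplier applies. Age 60, serum urea nitrogen (SUN) 16 mg/dl, albumin 4.0 g/dl. MDRD GFR (ml/min/1.73 m²) is taken as comparable to creatinine clearance (ml/min).

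**Criterion 1 alone.** With baseline GFR B, the criterion is met at B − 25. This is below 50 whenever B is below 75. For B = 50, 60 and 70 it is met at 25, 35 and 45.

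**Printed formula.** GFR = 170 × Cr^-0.999 × age^-0.176 × SUN^-0.170 × Alb^0.318. With the assumed values, 170 × 0.4865 × 0.6242 × 1.5540 = 80.2, so GFR = 80.2 × Cr^-0.999. GFR reaches 50 at creatinine 1.61 in every row below.

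| Baseline creatinine | Baseline GFR | Rise needed to reach GFR 50 | GFR when the 25-unit fall is met | GFR when the 0.5 rise is met |
|---|---|---|---|---|
| 1.0 | 80.2 | 0.61 | 55.2 | 53.5 |
| 1.1 | 72.9 | 0.51 | 47.9 | 50.2 |
| 1.2 | 66.9 | 0.41 | 41.9 | 47.2 |
| 1.3 | 61.7 | 0.31 | 36.7 | 44.6 |

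At 1.2 and 1.3 the patient is below 50 before either criterion is met. At 1.1 the 0.5 rise comes just before 50, although the 25-unit fall does not. At 1.0 both are met above 50.

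**Other ages, same formula.**

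- Age 70, SUN 18, albumin 3.8, creatinine 1.3: GFR 57.9. It reaches 50 after a rise of 0.21, and the 25-unit fall is met at 32.9. At creatinine 1.0 that fall is met at 50.3, just above 50.
- Age 45, SUN 16, albumin 4.0: the 25-unit fall is met at 59.4 for creatinine 1.0 and at 51.7 for 1.1, so there is no gap at either value.

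**Criterion 3 as a stop.** The 0.5 rise brings only monitoring at Grade 1. Appendix B puts Grade 2 above 1.5 times the upper limit of normal, which the documents do not state. If it is 1.2 to 1.4 mg/dl, Grade 2 starts above 1.8 to 2.1 mg/dl (1.5 × 1.2 and 1.5 × 1.4). Both exceed the 1.61 at which the 60-year-old's GFR is already 50.

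**Criterion 2.** This is a matter of text. It can lead to a measured clearance at any time, but the protocol does not say which calculated GFR counts as abnormal, or what follows from a low clearance without Fanconi's syndrome.

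**The case against.** The strongest reply is that the two parts of Section G add to each other. The list does not claim to be exhaustive, and the statement about 50 ml/min covers all patients and sits in the same dose-modification section. Item 2 would very plausibly be triggered by a calculated GFR below 50 and would then measure clearance on demand. Section F leaves room to stop for declining renal function, and Section D for persistent moderate side effects attributed to the drug.

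Much of this stands. A reader might infer that the protocol keeps patients with low renal reserve on full daily dosing below 50. The documents do not support that: no passage orders treatment to continue unchanged after an evaluation that does not show Fanconi's syndrome. A reader might also infer that clearance can be known only at weeks 48 and 192. Those are the scheduled on-treatment measurements, but item 2 can prompt others.

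The affected examples also lie near the creatinine limit for entry, and at 1.0 the gap is absent at all three ages tried. Whether an absolute 25-unit fall is a good rule is a clinical judgement and not part of this point.

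The reply does not supply the missing link. Even on the cumulative reading, no passage ties the 50 ml/min level to a stated action in the list, none gives the adjusted interval, and Section F refers back to text that lacks the level.

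**Conclusion.** The point holds as an unreconciled safety threshold. Section G states a level at which dosing must change, and its criteria for dose adjustment or cessation do not use it. Some eligible patients can cross it without meeting criterion 1 or 3. Under the age-60 assumptions this happens at baseline creatinine 1.2 to 1.3 mg/dl and not at 1.0.

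The size in this trial is unknown, because the documents do not give the share of patients with baseline values in that range. The figures rest on assumed laboratory values and on treating MDRD GFR and creatinine clearance as one scale. The conflict between the passages does not depend on either assumption.

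**What to change.** Reconcile the two parts of Section G, together with Section B item 13, the clearance schedule in Section E and the toxicity rule in Section F. The amended text should state:

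- whether the 50 ml/min level governs dosing on study or is background information;
- which renal measure it refers to, measured creatinine clearance or calculated GFR;
- how it relates to the three listed criteria, including what counts as abnormal in item 2 and what follows when the evaluation does not show Fanconi's syndrome.

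The sponsor decides the clinical rule and the action. The cost is a wording amendment, and possibly a few more renal evaluations or dose changes. The blood tests that the printed formula needs are already drawn at each visit under Section E.
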